14.2.2 Assessment of AEs

The investigator must assess all AEs using the following criteria:

14.2.2.1 Severity

The term severity is described as the intensity grade or level for a specific event, i.e., mild, moderate, severe. Importantly, severity is *not* the same as seriousness, which is based on participant/event *outcome or action* criteria usually associated with events that pose a threat to a subject's life or functioning (ICH E2A). The following definitions should be used to assess the severity of adverse events:

- Mild: an AE that is easily tolerated
- Moderate: an AE sufficiently discomforting to interfere with daily activity
- **Severe:** an AE that prevents normal daily activities

14.2.2.2 Causal Relationship

The relationship between an adverse event and the test article will be determined by the investigator on the basis of his/her clinical judgment using the following definitions:

Sponsor Name: Actavis, LLC Protocol: 094-3153-301, v1.0

Certain - A clinical event that definitely:

• follows a reasonable time relationship to drug administration.

- follows a known or expected response pattern to the suspected medicine.
- cannot be explained by an alternate factor (e.g. concurrent disease, drug, chemicals).
- follows a clinically reasonable response on withdrawal of the suspected drug.
- reappears on re-challenge with the offending drug.

Probable - A clinical event where association of the event with the study drug seems likely and that:

- follows a reasonable time relationship to drug administration.
- follows a known or expected response pattern to the suspected medicine.
- is unlikely to be attributed to an alternate factor (e.g. concurrent disease, drug, chemicals).
- follows a clinically reasonable response on withdrawal of the suspected drug.

(Re-challenge information is not required to fulfill this definition).

Possible - A clinical event where a relationship between drug and event cannot be ruled out and that:

- follows a reasonable time relationship to drug administration.
- follows a known or expected response pattern to the suspected medicine.
- can be produced by a number of other factors (e.g. concurrent disease, drug, chemicals).

Not Related- A clinical event that is clearly not related to the use of the study drug and that:

- does not follow a reasonable time relationship to drug administration.
- does not follow a known or expected response pattern to the suspected medicine.

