14. ADVERSE EVENT REPORTING

14.1 Definitions

The following definitions will be utilized:

Adverse Event (AE) - Any untoward medical occurrence associated with the use of a drug in humans, whether or not considered drug related. An AE can therefore be any unfavorable and unintended sign (including an abnormal laboratory finding, for example), symptom, or disease temporally associated with the use of a test article, whether or not considered related to the test article.

Adverse Drug Reaction (ADR) - Any adverse event caused by a drug. Adverse reactions are a subset of all suspected adverse reactions for which there is reason to conclude that the drug caused the event.

Suspected Adverse Reaction (SAR) – Any AE for which there is a reasonable possibility that the drug caused the event. A "reasonable possibility" means that there is evidence to suggest a causal relationship between the drug and the adverse reaction.

Serious Adverse Event (SAE) - Any untoward medical occurrence that at any dose in the view of either the investigator or the Sponsor:

- Results in death
- Is life-threatening (i.e., its occurrence places the patient or subject at immediate risk of death),

Sponsor Name: Actavis, LLC Protocol: 094-3153-301, v1.0

• Requires inpatient hospitalization or prolongation of existing hospitalization with the following exceptions:

- Hospitalization for preplanned treatment for an existing condition
- Hospitalization for social reasons (in countries which permit such hospitalization)
- Hospitalization required for protocol-required-testing or efficacy measurement.
- Results in persistent or significant incapacity or substantial disruption of the ability to conduct normal life functions, or
- Is a congenital anomaly/birth defect
- Important medical event

Important medical events that may not result in death, be life-threatening, or require hospitalization may be considered a serious adverse drug experience when, based upon appropriate medical judgment, they may jeopardize the patient or patient may require medical or surgical intervention to prevent one of the outcomes listed in this definition. Examples of such medical events include allergic bronchospasm requiring intensive treatment in an emergency room or at home, blood dyscrasias or convulsions that do not result in hospitalization, or the development of drug dependency or drug abuse.

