Unexpected adverse drug reaction: An AE, whether serious or non-serious, is designated an unexpected (unlabeled) drug related event if it is not consistent with the risk information in the Investigator Brochure, general investigational plan or Package Insert (marketed drugs) or if the event is shown to have a materially greater frequency or severity than previously reported; then such event(s) will be reported to the investigators if, in the opinion of the medical monitor, such findings represent a material drug related event.

Test article: A pharmaceutical form of an active ingredient (or "primary operational component" for devices) or vehicle/placebo being tested or used as a reference in the study, whether blinded or unblinded.

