14.2.4 IRB/IEC Notification by Investigator

Reports of all serious adverse events (including follow-up information) must be submitted to the Institutional Review Board (IRB)/Independent Ethics Committee (IEC) according to local requirements. Copies of each report and documentation of IRB/IEC notification and receipt will be kept in the Clinical Investigator's Regulatory binder.

As required, will notify investigators of all AEs that are serious, unexpected, and certainly, probably or possibly related to the test article. This notification will be in the form of a Safety Update to the Investigator Brochure (i.e., "15-day letter").

Upon receiving such notices, the investigator must review and retain the notice with the Investigator's Brochure and immediately submit a copy of this information to the responsible IRB according to local regulations. The investigator and IRB will determine if the informed consent requires revision. The investigator should also comply with the IRB procedures for reporting any other safety information. Where required, submission of Safety Updates by the investigator to Health Authorities should be handled according to local regulations.

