14.2.5 FDA Notification by Sponsor

The study Sponsor shall notify the FDA of any unexpected fatal or life-threatening experience associated with the use of the drug as soon as possible but no later than seven (7) calendar days from the Sponsor's original receipt of the information followed by as complete a report as possible within 8 additional calendar days. This report must include an assessment of the importance and implication of the findings, including relevant previous experience with the same or similar medicinal products.

Serious, unexpected reactions (ADRs) that are not fatal or life-threatening must be filed as soon as possible but no later than 15 calendar days after first knowledge by the Sponsor that the case meets the minimum criteria for expedited reporting.

If a previous adverse event that was not initially deemed reportable is later found to fit the criteria for reporting, the study Sponsor will submit the adverse event in a written report to the FDA as soon as possible, but no later than 15 calendar days from the time the determination is made.

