8.8 Safety Analyses

8.8.1 Adverse Events

Verbatim terms on the CRFs will be mapped into system organ class and preferred terms using MedDRA Coding Dictionary version 16.0. Tabulations of the number of subjects experiencing adverse events will be presented by System Organ Class (SOC) and Preferred Term (PT) and treatment group for (a) adverse events, (b) adverse events by maximum severity and (c) adverse events by closest relationship to study drug. Adverse events will be counted only once for a subject within each Preferred Term and System Organ Class; thus, since a subject may have more than one Preferred Term within an SOC, percentages of PT may not sum to the percentage in the SOC. If a subject reports a PT multiple times with differing severities, only the most severe is counted. If a subject reports a PT multiple times with differing relationships to study medication, only the one most related to study medication is counted based on the following order: certain, probable, possible, and not related.

Fisher's Exact tests will be performed on adverse events with a 2% or greater frequency to facilitate evaluation of potential safety differences among treatments.

Serious adverse events will be listed separately for systemic AEs, if applicable.

[figure not shown]

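### All three related causality grades require a known reaction pattern, so a new type of reaction that closely follows dosing fits no grade

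*Protocol*

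**What the plan says.** Protocol 14.2.2 requires every adverse event to be assessed against set criteria. Section 14.2.2.2 has the investigator grade causality "on the basis of his/her clinical judgment using the following definitions". There are four grades:

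- **Certain, Probable and Possible** each list a reasonable time relationship and the condition that the event "follows a known or expected response pattern to the suspected medicine". They differ on alternative causes, response to withdrawal and re-challenge.
- **Not Related** is for an event that is clearly unrelated, has no reasonable time relationship, and "does not follow a known or expected response pattern to the suspected medicine".

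SAP 6.2.3 repeats the four grades and adds no other.

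Other sections use relatedness or define terms close to it:

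- Protocol 14.1 defines a suspected adverse reaction by a reasonable possibility of causation, meaning that "there is evidence to suggest a causal relationship between the drug and the adverse reaction".
- Protocol 14.1 calls an event unexpected if "it is not consistent with the risk information in the Investigator Brochure, general investigational plan or Package Insert (marketed drugs"), or if it proves materially more frequent or more severe than reported before.
- Protocol 14.2.4 provides a duty to "notify investigators of all AEs that are serious, unexpected, and certainly, probably or possibly related to the test article".
- Protocol 14.2.5 words the 15-day FDA rule as "Serious, unexpected reactions (ADRs) that are not fatal or life-threatening must be filed as soon as possible". Section 14.1 makes ADRs a subset of suspected adverse reactions.
- SAP 8.8.1 keeps a subject's most related report of each preferred term, "based on the following order: certain, probable, possible, and not related".

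**The concern.** The trial tests a newly developed generic formulation (Protocol 2), and safety is part of its objective (Protocol 3). A reaction that belongs to the new product and is absent from the reference label is one that causality assessment should be able to recognise. The scale asks whether the event looks like something already known before it can be called related at all.

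The grade has several uses. It decides whether an event meets the 14.2.4 notice, and it fills the table by closest relationship (Protocol 17.3.2.2 and SAP 8.8.1). Relatedness also matters in 14.2, where a finding of no relation is one of the points that can end follow-up; in 13.2, where follow-up to resolution after withdrawal is tied to treatment-related events; and in 14.2.3.1, where reporting of a serious event after the study period depends on a possible relation.

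**Working it through.** The plan gives no figure on this point, so there is none to reproduce. The check is one of logical coverage.

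**Inputs.** The bullets of each grade in Protocol 14.2.2.2. Each event is described by timing (plausible or not) and pattern (known or not). Within each of those four combinations there are 3 levels of alternative cause (cannot explain the event, unlikely, can produce it) × 2 for response to withdrawal × 2 for re-challenge = 12 profiles.

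**Rules applied.** All three related grades need plausible timing and a known pattern. In addition:

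- Certain needs an alternative cause that cannot explain the event, a withdrawal response and re-challenge.
- Probable needs an alternative cause that is at most unlikely, and a withdrawal response.
- Possible needs an alternative cause that can produce the event.
- Not Related needs implausible timing and no known pattern. The bullets follow a lead-in ending in *and that*, so both apply. Reading them as alternatives is shown for comparison.

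| Timing plausible | Known pattern | Both Not Related bullets needed (as written) | Either bullet enough |
|---|---|---|---|
| Yes | Yes | 8 related, 4 no grade | 8 related, 4 no grade |
| Yes | No | 12 no grade | 12 Not Related |
| No | Yes | 12 no grade | 12 Not Related |
| No | No | 12 Not Related | 12 Not Related |

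The 8 related profiles are 4 that meet Probable (1 of them also Certain) and 4 that meet Possible. The 4 without a grade have no likely alternative cause and no withdrawal response.

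For a time-plausible event without a known pattern, 0 of 12 profiles reach a related grade on either reading. As written, all 12 have no grade.

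**Against the 14.2.4 notice.** The notice needs a serious event that is unexpected and has a related grade. An event unexpected because it is of a new type has no known pattern, so it cannot have a related grade. An event of a known type that is unexpected because it is more frequent or more severe can: 8 of 12 profiles.

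**What a change would do** for time-plausible events without a known pattern:

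- Pattern condition removed from Possible only: 4 of 12 gradable. The 8 left out include those with no likely alternative cause that respond to withdrawal, which are the strongest new signals.
- Removed from all three related grades: 4 + 4 = 8 of 12.
- Also making Possible the default when timing is plausible and a relationship cannot be excluded: 8 + 4 = 12 of 12.

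These counts show which combinations have a grade. They are not probabilities of events.

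**The case against.** The strongest reply is that sites will not treat the bullets as a checklist. Grading rests on clinical judgment, and the lead-in to Possible, a relationship that cannot be excluded, suits a novel event well. This has weight in practice, but the judgment must use the listed definitions and the lead-in is joined to the bullets. A site that grades such an event Possible departs from the text, so sites may differ.

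The other objections limit how far the point reaches, and they stand:

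- A reader might infer that the 14.2.4 rule is left almost empty. The documents do not support that. The frequency or severity limb works, and a reaction typical of the drug but absent from the risk documents arguably has a known pattern and is still unexpected. Nothing in the documents shows how events would divide between these routes. Section 14.1 also has unexpected events reported to investigators when the medical monitor considers them material and drug related, without naming the grades.
- A reader might infer that serious novel events escape reporting. Within the reporting period, sites report all serious events whatever the relation (14.2.1), by form within 24 hours (14.2.3.1), and to the IRB under local requirements (14.2.4). The FDA rules in 14.2.5 do not name the four grades, so any effect there is indirect.
- A reader might infer that sites will enter Not Related and so bias the generic-versus-reference comparison toward no difference. The event fails Not Related on timing and on its lead-in, so that choice is not forced. Possible is at least as natural, and the direction is unknown. The overall and by-severity tables and the Fisher tests in SAP 8.8.1 ignore relatedness, and local skin reactions are scored separately without a causality grade (Protocol 10.2).

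**Conclusion.** The scale in Protocol 14.2.2.2 is wrong as written. A new type of reaction that closely follows dosing fits none of the four grades (0 of 12 profiles related, 12 of 12 without a grade). This contradicts the suspected adverse reaction definition in 14.1 and prevents the novel-event limb of unexpected from meeting the grade-based notice in 14.2.4.

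The effect is confined to those notices, to the uses of relatedness in 13.2, 14.2 and 14.2.3.1, and to the descriptive table by closest relationship, which has no row for an ungraded event. The documents give no rate for novel serious reactions, so the number affected cannot be calculated. I assume it is small among about 435 subjects.

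The conclusion rests on reading the bullets of each grade as jointly required. If either Not Related bullet were enough, the event would be Not Related instead of ungraded, and still could not be called related.

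**What to change.** In Protocol 14.2.2.2:

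- Make a known pattern a supportive feature, not a requirement, in Certain, Probable and Possible.
- Make Possible the default whenever timing is plausible and a relationship cannot be excluded, without requiring that other factors could produce the event.
- Define Not Related as an implausible time relationship or a clear alternative cause, with no pattern condition. State that a clear alternative cause is one that allows a drug relationship to be excluded, so that this grade does not overlap with Possible.

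In 14.2.5, bring the ADR wording into line with the suspected adverse reaction definition in 14.1. This is a related mismatch that does not come from the scale itself.

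The cost is wording in two protocol sections and the CRF completion guidance. Design, sample size and the SAP ordering of grades stay as they are. The downside is a few more events graded Possible and a few more expedited reviews.

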14.2.2.3 Outcome

An AE outcome is defined as follows:

- Fatal Termination of life as a result of an AE.
- Not Recovered/Not Resolved AE has not improved or recuperated.
- Recovered/Resolved with Sequelae Subject recuperated but retained the pathological conditions resulting from the prior disease or injury.
- Recovered/Resolved AE has improved or recuperated.
- **Recovering/Resolving** AE is improving.
- Unknown Not known, not observed, not recorded or refused.

Sponsor Name: Actavis, LLC Protocol: 094-3153-301, v1.0

14.2.2.4 Treatment Required

• Yes (if yes, specify on concomitant therapy page of the CRF)

• No

14.2.3 Procedure for Reporting of Serious Adverse Events

14.2.3.1 Notification by Investigator to

A Serious Adverse Event (SAE) form must be completed by the investigator and faxed to the Medical Monitor or Project Manager noted on page 1 of the protocol within 24 hours after becoming aware of the event. The investigator will keep the original of this SAE form on file at the study site. The Medical Monitor will inform the Sponsor within 24 hours of their notification of the event. At the time of the initial report, the following information should be provided at a minimum:

- o Study identifier
- o Study Center
- o Subject Number
- o A description of the event
- o Date of onset
- Date investigator was informed of the event
- Current status

- Whether study treatment was discontinued
- The reason why the event is classified as serious
- Investigator assessment of the association between the event and trial treatment
- Blinding status (randomization code broken or not) of subject
- o If the Test Article was administered and date of the administration

Even if all the information is not known, an initial report should be made. The investigator is obliged to provide follow-up information within 3 days of the initial report on a Serious Adverse Event form, and any other diagnostic information that will assist the understanding of the event.

Significant new information on ongoing serious adverse events should be provided promptly to the Medical Monitor or Project Manager as a follow-up report.

Documents relevant to the diagnosis, treatment and course of the event must be submitted (e.g. technical investigation reports, histology findings, case report forms, hospital discharge documents). All documents must be blinded with respect to subject's name.

When the investigator determines that there is no more information likely to be available, a final report should be provided.

Serious adverse events that are still ongoing at the end of the study period must be followed up to determine the final outcome, if possible (see Section 14.2). Any serious

Sponsor Name: Actavis, LLC Protocol: 094-3153-301, v1.0

adverse event that occurs after the study period and is considered to be possibly related to the study treatment or study participation should be recorded and reported to the Medical Monitor within 24 hours.

14.2.4 IRB/IEC Notification by Investigator

Reports of all serious adverse events (including follow-up information) must be submitted to the Institutional Review Board (IRB)/Independent Ethics Committee (IEC) according to local requirements. Copies of each report and documentation of IRB/IEC notification and receipt will be kept in the Clinical Investigator's Regulatory binder.

As required, will notify investigators of all AEs that are serious, unexpected, and certainly, probably or possibly related to the test article. This notification will be in the form of a Safety Update to the Investigator Brochure (i.e., "15-day letter").

Upon receiving such notices, the investigator must review and retain the notice with the Investigator's Brochure and immediately submit a copy of this information to the responsible IRB according to local regulations. The investigator and IRB will determine if the informed consent requires revision. The investigator should also comply with the IRB procedures for reporting any other safety information. Where required, submission of Safety Updates by the investigator to Health Authorities should be handled according to local regulations.

14.2.5 FDA Notification by Sponsor

The study Sponsor shall notify the FDA of any unexpected fatal or life-threatening experience associated with the use of the drug as soon as possible but no later than seven (7) calendar days from the Sponsor's original receipt of the information followed by as complete a report as possible within 8 additional calendar days. This report must include an assessment of the importance and implication of the findings, including relevant previous experience with the same or similar medicinal products.

Serious, unexpected reactions (ADRs) that are not fatal or life-threatening must be filed as soon as possible but no later than 15 calendar days after first knowledge by the Sponsor that the case meets the minimum criteria for expedited reporting.

If a previous adverse event that was not initially deemed reportable is later found to fit the criteria for reporting, the study Sponsor will submit the adverse event in a written report to the FDA as soon as possible, but no later than 15 calendar days from the time the determination is made.

14.3 Laboratory Test Abnormalities

Although there are no specific labs required in this study, any laboratory test result that meets the criteria for a Serious Adverse Event (see Section 14.2) must also be reported as

Sponsor Name: Actavis, LLC Protocol: 094-3153-301, v1.0

a SAE so can collect additional information about that abnormality, including information regarding relationship to test article or other causes, any action taken, and resolution.

